Xbox Kinect™ to Promote Physical Fitness and Lean Mass in Severely Burned Children: A Randomized Controlled Trial

4-4-2020

Study Protocol

Background: Burns lead to persistent and detrimental muscle breakdown and weakness and poor physical fitness so Rehabilitation following burns is integral to improving physical and psychological outcomes. This study was undertaken to evaluate an alternative exercise rehabilitation strategy, so the aim of this work involving To explore the outcomes of an Xbox Kinect intervention on muscle strength, lean body mass (LBM) and cardiopulmonary fitness in severe pediatric burn.

Methods: Forty burned children with burns covering 40–60% of the total body surface area (TBSA), aged 10–16 years, were randomized into the standard of care (n=20), and Xbox training group (n=20) groups. All burned children received 12 weeks of routine physical therapy program (RPTP). In addition, the Xbox group received Xbox training involving five games for 50min a day, three times a week for 12 weeks .Outcomes were leg muscle strength was assessed as peak torque using a Biodex Isokinetic Dynamometer, Oxygen consumption capacity, measured as peak VO₂, was studied using a modified Bruce treadmill protocol, and lean body mass was determined using dual-energy X-ray absorptiometry. Outcomes were measured at baseline and after 12 weeks of intervention.

Conclusion: These findings suggest that the use of XbK intervention is a valuable, feasible and pleasant approach in order to improve muscle strength, lean body mass (LBM) and cardiopulmonary fitness in severe pediatric burn Xbox Kinect virtual reality could offer as a therapeutic and motivational tool when used with children burn.

Keywords: Severely burned children, interactive video games, Xbox Kinect™ ; lean body mass; VO₂ Peak; muscle strength; Enjoyment.

Statistical Analysis Plan

Reported data was analyzed using Statistical Package for Social Sciences (SPSS) computer program (version 23 windows) (Charles R Flint, New York, USA). Normality test of data using Shapiro-Wilk test was used, that reflect the data was normally distributed. There were no univariate or multivariate outliers, as assessed by boxplot and Mahalanobis distance ($p > 0.05$), respectively; there were linear relationships, as assessed by scatterplot; no multicollinearity. There was homogeneity of variances ($p > 0.05$), as assessed by Levene's test of homogeneity of variances. So, parametric analysis was performed.

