Potential differences in baseline demographic between groups were examined using independent sample t-tests. 2x2 mixed design MANOVA was used to examine the effect of

treatment on the measured dependent variables (LBM, trunk, leg, Vo2 and PT) within group as the between-subject variable (experimental received and control received), and time as the within-subject variable (pre and post treatment). The variable of interest was the group-by- time interaction at an a priori alpha level of 0.05 and 95 % confidence interval.

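### The only efficacy rule is a five-variable MANOVA interaction at 0.05, which cannot show which outcome improved, yet the protocol claims benefit in three separate domains

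*Combined protocol and SAP*

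**What the plan says.** The Statistical Analysis Plan gives one efficacy analysis: "2x2 mixed design MANOVA was used to examine the effect of" treatment on five dependent variables, listed as "LBM, trunk, leg, Vo2 and PT". Group is the between-subject factor and time (before and after treatment) the within-subject factor. The effect of interest is the group-by-time "interaction at an a priori alpha level of 0.05 and 95 % confidence interval". The only other comparison between groups is a set of t-tests on baseline demographics.

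The plan does not state a primary outcome, univariate follow-up tests, a contrast for any single outcome, a testing order or a multiplicity adjustment. Trunk and leg are not defined.

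The Study Protocol's Background sets the aim as "To explore the outcomes of an Xbox Kinect intervention on muscle strength, lean body mass (LBM) and cardiopulmonary fitness". Its Methods name three outcomes: leg peak torque, peak VO2 and lean body mass by DXA. Its Conclusion calls the intervention a valuable "approach in order to improve muscle strength, lean body mass (LBM) and cardiopulmonary fitness in severe pediatric burn".

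**The concern.** The rule and the claims are on different levels. The interaction is a single test of whether the two groups' mean changes differ anywhere in a five-dimensional vector. Rejecting it does not identify which component differs, or in which direction, and it produces no single treatment difference to which a 95% interval could belong. The Conclusion nevertheless speaks of three domains one by one.

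Two things are at stake. First, an effect confined to one outcome would satisfy the only stated rule and could be read as benefit in all three. Second, if the authors move from a significant MANOVA to ordinary univariate tests, the MANOVA limits error at 5% only when nothing responds. Once one outcome truly responds, it will usually be significant and gives the remaining outcomes little protection.

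**Working it through.** **Inputs from the documents.** 20 children per arm, two time points, five dependent variables, alpha 0.05 (Study Protocol, Methods; Statistical Analysis Plan). The documents give no effect size, SD, correlation or power, so there is no figure of theirs to reproduce.

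**The test.** With two groups and two time points, the MANOVA interaction is Hotelling's T² on the five change scores:

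F = T² × (2n − p − 1) / [p(2n − 2)] = T² × 34 / (5 × 38), on (5, 34) df, with critical value 2.494.

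This yields one p-value for all five variables together.

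**Error with unadjusted follow-up tests, if the MANOVA is always significant and outcomes are independent.**
- Two null outcomes (LBM, VO2): 1 − 0.95² = 0.0975.
- Four null outcomes (adding trunk and leg): 1 − 0.95⁴ = 0.185.

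**Simulation.** Assumptions, none of them from the documents: only peak torque responds, by d = 1.0 or 1.5 SD of change. Outcomes are either independent, or the three lean-mass variables (taking trunk and leg as lean-mass measures) correlate 0.8 or 0.9 with each other and all other pairs 0.3. There are 40,000 runs per scenario. Follow-up t-tests have 38 df and are two-sided at 0.05. Each cell shows d = 1.0 / d = 1.5; the false-positive rows with follow-up tests count only runs in which the MANOVA was significant.

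| Quantity | Independent | 0.8 / 0.3 | 0.9 / 0.3 |
|---|---|---|---|
| MANOVA rejects | 0.597 / 0.939 | 0.681 / 0.972 | 0.677 / 0.971 |
| Given rejection, all three claimed outcomes significant for Xbox | 0.001 / 0.001 | 0.003 / 0.002 | 0.004 / 0.002 |
| Given rejection, neither LBM nor VO2 significant for Xbox | 0.930 / 0.948 | 0.938 / 0.952 | 0.938 / 0.952 |
| False positive on LBM or VO2, two-sided | 0.080 / 0.096 | 0.083 / 0.094 | 0.083 / 0.095 |
| Same, favouring Xbox only | 0.040 / 0.049 | 0.042 / 0.047 | 0.042 / 0.048 |
| False positive on any of four null variables, two-sided | 0.152 / 0.180 | 0.120 / 0.139 | 0.108 / 0.127 |
| Same, favouring Xbox only | 0.079 / 0.093 | 0.060 / 0.069 | 0.055 / 0.064 |
| Holm over three: false positive on LBM or VO2, two-sided | 0.043 / 0.048 | 0.044 / 0.048 | 0.044 / 0.048 |
| Same, favouring Xbox only | 0.022 / 0.024 | 0.023 / 0.024 | 0.024 / 0.024 |

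When no outcome responds, a significant MANOVA followed by at least one significant univariate test occurs in 0.045, 0.038 and 0.036 of runs in the three structures. The MANOVA does its job in that case.

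**Power cost of Holm.** Two-sample t-test on change, 38 df, noncentrality d × √(n/2) = d × √10.
- Alpha 0.05: 80% power at d = 0.909; power at d = 1.0 is 0.869.
- Alpha 0.05/3 = 0.0167, Holm's first step: 80% power at d = 1.064; power at d = 1.0 is 0.742.

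Later Holm steps use 0.025 and 0.05, so these are the worst case.

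**The case against.** - **Another reading is possible.** A confidence interval makes sense only for a single outcome, so the authors may have meant one interaction test per variable. The text does not say so, and that reading does not rescue the plan. It would leave five tests at 0.05 with no adjustment: 1 − 0.95⁵ = 0.226 if independent. The same fix covers both readings.
- **The scenario is the least favourable one.** That all three outcomes are rarely significant together follows from setting the LBM and VO2 effects to zero, and nothing in the documents supports an effect on peak torque alone. If all five variables respond equally, all three claimed outcomes are significant for Xbox, given rejection, in about 33-55% of runs at d = 0.8, 66-76% at d = 1.0 and 99% at d = 1.5. This stands. The simulation shows that the test is non-specific; it does not estimate how often this trial would mislead.
- **The inflation is modest for the claims made.** Only benefit is claimed, so the relevant rate is 4-5% against a directional 2.5%: up to a doubling, but not above 5%. The 11-18% range includes trunk and leg, for which no separate claim is made. Both points are fair.
- **A correlation of 0.9 sits uneasily with the plan's report of no multicollinearity.** No threshold is given, and results at 0.8 are nearly the same.
- **The wording is soft.** The aim is to explore and the Conclusion says the findings suggest. That tempers the claims but does not supply a test for them.
- **Holm is one choice among several.** A single named primary outcome or a fixed testing order would also close the gap. True, although after the analysis neither could be shown to have been chosen independently of the results.

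**Conclusion.** The concern holds, and it rests on the text rather than on the simulation. The plan's one decision rule cannot support three outcome-level conclusions, and no outcome has a specified contrast or interval. The MANOVA itself is valid as a global test at 5%.

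The numerical size depends on assumed effects and correlations and, for the error rates, on the inference that unadjusted univariate tests would follow. On those terms, error on LBM or VO2 is roughly twice nominal in the favourable direction. This should be fixed, but it does not invalidate the trial.

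**What to change.** 1. For LBM, peak VO2 and peak torque, report the between-group difference in change with its 95% CI.
2. Test the three with Holm at an overall two-sided 0.05, and claim benefit only for those that pass. State that the intervals are unadjusted and that claims rest on Holm.
3. Define trunk and leg and treat them as exploratory. Keep the MANOVA as supportive.
4. Limit the Conclusion to the outcomes that pass.

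The plan is in the past tense and already reports assumption checks ("Normality test of data using Shapiro-Wilk test was used, that reflect the data was normally distributed"), so the data may have been analysed. If so, label the Holm family post hoc; the change cannot restore pre-specification.

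The cost is a few lines of text and one results table, with no new data, plus the power loss shown above: at a true difference of 1.0 SD, from 87% to no less than 74% for any one outcome.

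### The SAP attaches a 95% confidence interval to a five-variable omnibus interaction and names no per-outcome contrast, so as written it yields no estimate of how much Xbox adds

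*Combined protocol and SAP*

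**What the plan says.** The Statistical Analysis Plan describes one analysis of the outcomes: "2x2 mixed design MANOVA was used to examine the effect of" "treatment on the measured dependent variables (LBM, trunk, leg, Vo2 and PT"). Arm is the between-subject factor, and the other factor is "time as the within-subject variable (pre and post treatment"). The target is then named: "The variable of interest was the group-by- time interaction". The same sentence attaches the error level and the interval to it: "interaction at an a priori alpha level of 0.05 and 95 % confidence interval".

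The only other comparison in the SAP is a set of t-tests on baseline demographics. Neither the Study Protocol nor the SAP names a mean difference, a difference in change, an adjusted mean, an effect size or a follow-up contrast for any single outcome.

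The Study Protocol's Conclusion speaks outcome by outcome. It calls the intervention valuable and describes it as an "approach in order to improve muscle strength, lean body mass (LBM) and cardiopulmonary fitness".

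**The concern.** A confidence interval has to belong to a stated quantity. Here it is attached to a joint test of five variables, measured in different units, that returns an F statistic and a p-value. The 95% region that goes with this test is a five-dimensional ellipsoid, not a range in kilograms, torque or oxygen uptake.

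The effect size is what is at stake. A significant result would not show which of the five variables responded, whether the response favoured Xbox, or how large it was. A non-significant result with 20 children per arm would not show what size of benefit or harm remains possible. The Conclusion's separate statements about strength, lean mass and cardiopulmonary fitness, and its judgement of value, need exactly that information.

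**Working it through.** The documents give no power, SD, effect size or expected interval width, so there is no figure of the plan's own to reproduce.

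**Inputs.** From the Study Protocol, Methods: 20 children per arm, and two measurement times ("Outcomes were measured at baseline and after 12 weeks of intervention"). From the SAP: five dependent variables, alpha 0.05 and a 95% level. Assumed, because the documents do not say: all 40 children are analysed; the SD is equal across arms and visits; the pre/post correlation r lies between 0.3 and 0.9; and, in step 2 only, the five change scores all correlate at 0.5 with each other.

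**1. What the interaction test is.** With two visits, the group-by-time MANOVA on p = 5 variables is the two-sample Hotelling T² test on the five change scores.
- df = 20 + 20 − 2 = 38.
- F = T² × (df − p + 1)/(p × df) = T² × 34/190, on 5 and 34 df. On simulated two-arm, five-variable data, this conversion and a standard MANOVA routine both gave F = 3.2513.
- The 5% critical value is F = 2.4936, so the critical T² is 2.4936 × 190/34 = 13.93.

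**2. What a p-value of 0.05 leaves open.** Let d be the vector of between-arm differences in mean change, in SDs of change, and R the correlation matrix. Then T² = (20/2) d′R⁻¹d = 10 d′R⁻¹d. With all correlations 0.5, R⁻¹ = 2(I − J/6), where J is the matrix of ones.
- One variable differs by δ, the rest by nothing: d′R⁻¹d = (5/3)δ², so δ = √(13.93/16.67) = 0.91, with either sign.
- All five differ by δ: again (5/3)δ², so δ = 0.91.
- One differs by +δ and another by −δ: 4δ², so δ = √(13.93/40) = 0.59.

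A gain on one variable, a loss on one variable, a gain on all five, and a gain on one offset by a loss on another all give exactly p = 0.05.

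**3. The interval that does exist.** For a single variable the interaction has 1 df and equals the between-arm difference in mean change. Its standard error is √(2/20) = 0.3162 SD of change.
- Unadjusted 95%: t(38) = 2.0244, half-width 2.0244 × 0.3162 = 0.64.
- Bonferroni over five: t(38) = 2.7116, half-width 0.86.
- T² simultaneous: √13.93 × 0.3162 = 1.18.

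**4. The same in SDs of the raw measurement.** Change score: 0.640 × √(2(1 − r)). Baseline-adjusted, ignoring chance baseline imbalance: t(37) × 0.3162 × √(1 − r²), with t(37) = 2.0262. Unadjusted 12-week difference: 0.64 whatever r is.

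| r (assumed) | Change score | Baseline-adjusted | 12-week difference |
|---|---|---|---|
| 0.3 | 0.76 | 0.61 | 0.64 |
| 0.5 | 0.64 | 0.55 | 0.64 |
| 0.7 | 0.50 | 0.46 | 0.64 |
| 0.9 | 0.29 | 0.28 | 0.64 |

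**The case against.** The strongest reply is that the SAP already points at the right comparison. It names the interaction, and for each outcome that interaction is an ordinary contrast with an ordinary 95% interval in the outcome's own unit. A generous reader would take the sentence to mean those five contrasts. This stands in part: the interval exists and needs no new method. But the SAP does not say that the interval is per outcome, and the analysis it describes is the joint one. If the phrase is only loose wording for a 95% confidence level, the plan contains no interval at all, and the missing effect estimate remains.

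Three stronger readings are tempting, and the documents do not support them.

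- A reader might infer that no interval exists for the effect. Step 3 above shows otherwise: the joint region, simultaneous intervals and single-outcome intervals all exist. The defect is that none is specified.
- A reader might infer that the trial will judge Xbox by change within one arm, or by whether the two arms' intervals overlap. Change within the Xbox arm would indeed be a poor guide, since "All burned children received 12 weeks of routine physical therapy program (RPTP") and both arms may improve. But no section plans either inference, and the SAP names the between-arm interaction as its target. Any error rate calculated for such practices would be hypothetical and would not measure a fault in this plan.
- A reader might infer that a between-arm interval at 12 weeks would be wrong. In a randomised trial it is a valid estimate of the treatment effect. It equals the change-score interval in width at r = 0.5 and is narrower below that (0.64 against 0.76 SD at r = 0.3). It is wider only when r exceeds 0.5.

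**Conclusion.** The point holds as a gap in what the plan estimates, and it deserves correction. Read literally, the analysis can establish that the arms differ in change on some combination of the five variables. It cannot say which variable moved, in which direction or by how much, so it does not by itself support the Conclusion's outcome-by-outcome statements.

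With 20 analysed per arm, the interval now left unspecified would have a half-width of 0.64 SD of change for each variable. On the raw scale this runs from 0.76 down to 0.29 SD for change scores as r goes from 0.3 to 0.9. Baseline adjustment gives about 0.55, 0.46 and 0.28 SD at r = 0.5, 0.7 and 0.9. These raw-scale figures depend on the assumed r and on equal SDs. The form of the test, F on 5 and 34 df, needs only the stated design and complete data.

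**What to change.** Keep the omnibus test and add to the Statistical Analysis Plan:

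*For each of the five dependent variables (LBM, trunk, leg, VO2, PT), the effect estimate is the between-arm difference (Xbox minus standard of care) at 12 weeks adjusted for that variable's baseline value, or the between-arm difference in change from baseline, in the unit of measurement, with its 95% confidence interval. Arm means at a visit and changes within one arm are descriptive only.*

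The final text should choose one of the two forms. Statements of size or value in the Conclusion should then rest on these intervals. The SAP is written in the past tense and already reports the results of its assumption checks, so any estimate chosen after the data were seen should be labelled post hoc.

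The cost is one sentence and one contrast per variable on data already collected, with no new patients or measurements. There are two downsides. The intervals will look wide with 20 children per arm. Five unadjusted intervals also do not control the family-wise error: if the five were independent, the chance that at least one wrongly excludes zero is 1 − 0.95⁵ = 0.23. Bonferroni over five would control it, at the price of a half-width of 0.86 instead of 0.64 SD of change. The SAP should state which is used.
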